## 4.2.4 Safety

### 4.2.4.1 Solicited Reactions

#### 4.2.4.1.1 Daily Intensity

All daily records for solicited reactions will be derived into daily intensity according to the following classification: None, Grade 1, Grade 2, Grade 3 or Missing for solicited administration site reactions; and None, Grade 1, Grade 2, Grade 3, or Missing for solicited systemic reactions.

For non-measurable solicited reactions, daily intensities will correspond to daily records reported in the clinical database and grade reported as “unknown” will be considered as “Missing”. When in the CRF presence is recorded as “No” and with all daily records missing then all daily intensities will be derived as “None”.

For measurable solicited reactions the daily measurements reported in the clinical database will be converted based upon the intensity scales defined in the Section 10.2.5 of the protocol. Note the intensity could be considered “None” (not a reaction) in the analysis despite being considered a reaction by the investigator.

Note: The maximum intensity on the ongoing period is derived from the record of the maximum intensity/measurement after the end of the solicited period following the rule described above.

#### 4.2.4.1.2 Maximum Intensity

Maximum overall intensity is derived from the daily intensities computed as described in [Section 4.2.4.1.1](#) and is calculated as the maximum of the daily intensities over the period considered.

#### 4.2.4.1.3 Presence

Presence is derived from the maximum overall intensity on the period considered:

- None: No presence
- Grade 1, Grade 2, Grade 3: Presence
- Missing or Unknown: Missing presence

Participants with at least one non-missing presence for a specific endpoint will be included in the analysis. Conversely, those without a non-missing presence will not be included in the analysis of the endpoint.

The time period is displayed as D01-D04, D05-D08, D09-D15, D16-D22, D23 or later.

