Safety 
• To assess the safety profile of the RSVt vaccine after each and any study intervention administration in pediatric participants.	Safety 
• Presence of any unsolicited systemic AEs reported in the 30 minutes after each study intervention administration• Presence of any solicited (ie, pre-listed in the participant's diary card [DC] and in the case report book [CRB]) administration site and systemic reactions within 21 days after each study intervention administration

Objectives	Endpoints
	
 • Presence of any unsolicited (spontaneously reported) AEs within 28 days after each study intervention administration • Presence of any AESIs within 28 days after each study intervention administration • Presence of any MAAEs within 28 days after each study intervention administration • Presence of any SAEs throughout the study
Transmission and virus shedding	Transmission and virus shedding

 • To describe the vaccine virus transmission in pediatric participants receiving placebo after the second study intervention administration 	
 • Presence of vaccine virus in D64 and D71 nasal swabs, detected by RSVt qRT-PCR in the pediatric participants receiving placebo
Exploratory	
    	    
	                           [figure not shown]Pediatric participants: Healthy infants / toddlers 6 to < 24 months of age in close contact with other infants / toddlers 6 to < 24 months of age who will participate in the studyAd-hoc close contact participants: Ad-hoc close contact children and adults who experience ARI in the 28 days following the administration of the study intervention to the close contact pediatric participant
Level and method of blinding	Observer-blind: 
Blinding for study intervention group assignment: participants, parents or LAR, outcome assessors, investigators, laboratory personnel, Sponsor study staffNo blinding for study staff who prepare and administer the study interventions
Study intervention assignment method	Pediatric participants will be screened for eligibility criteria at the time of inclusion and randomized to receive either RSVt vaccine or placebo in a 1:1 ratio. Randomization will be stratified by contact group (the household /group attended in daycare center) and by age group (< 12 months / ≥ 12 months)

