#### ***Solicited Reactions***

Number and percentage of participants with:

- Presence of solicited administration site reactions and systemic reactions occurring up to 21 days after each and any vaccination
- Each solicited reaction according to time of onset, maximum intensity, and number of days of occurrence and action taken
- Any solicited reaction leading to study discontinuation

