### 4.2.5.6 Adverse Events Leading to Study Discontinuation

A flag is available in the clinical database for all AEs in order to identify AEs leading to study discontinuation.

The items that are counted are:

- Disposition table: A subject who, on the “Completion at End of Study” form question “What was the subject's status?” has “Adverse Event” checked.
- Safety overview table: A participant who has either on the “Completion at End of Study” form question “What was the subject's status?” has “Adverse Event” checked, or lists a solicited AE that has “Caused Study Termination” checked that is at least Grade 1 or an unsolicited AE that has “Caused Study Discontinuation” checked that is at least Grade 1 or missing and is within the time period indicated.
- System Organ Class (SOC)/Preferred Term (PT) table: A solicited AE that has “Caused Study Termination” checked that is at least Grade 1 or an unsolicited AE that has “Caused Study Discontinuation” checked that is at least Grade 1 or missing and is within the time period indicated.

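### A non-measurable solicited reaction recorded as present in the CRF, but with no known daily grade, is dropped from the presence endpoint, while a CRF 'No' with missing records is kept

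*SAP*

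**What the plan says.** Protocol Section 3, Table 3.1, sets a secondary safety endpoint on the presence of any solicited "administration site and systemic reactions within 21 days after each study intervention administration". SAP Section 3.4.3.2 (Solicited Reactions) reports the number and percentage of participants with "Presence of solicited administration site reactions and systemic reactions occurring up to 21 days after each and any vaccination".

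The derivation is in SAP Section 4.2.4.1:

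- **4.2.4.1.1 Daily Intensity**, non-measurable reactions: a "grade reported as “unknown” will be considered as “Missing". The CRF presence answer appears in one rule only: "When in the CRF presence is recorded as “No” and with all daily records missing then all daily intensities will be derived as “None".
- **4.2.4.1.2 Maximum Intensity**: the maximum of the daily intensities. Nothing is said on how Missing ranks against None.
- **4.2.4.1.3 Presence**: taken from the maximum intensity. None means no presence, Grades 1 to 3 mean presence, and the last line is "Missing or Unknown: Missing presence". On the denominator, "those without a non-missing presence will not be included in the analysis of the endpoint".
- **3.4.6.1.3 Intensity**, the missing-data rule: for solicited reactions it only refers back to 4.2.4.1.1.

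Unsolicited AEs are handled differently. Under 4.2.4.2.1 an event needs a verbatim term and must not be Grade 0, so an ungraded event is kept. In 4.2.5.6 an unsolicited AE enters the discontinuation counts if it has the discontinuation flag "checked that is at least Grade 1 or missing and is within the time period indicated". A solicited AE enters through its own flag only if it is at least Grade 1.

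**The concern.** The endpoint asks whether a reaction occurred. The SAP answers from how severe it was graded, although Section 4.2.4.1.1 shows that the CRF also records presence directly. The SAP uses that answer in one direction only. A child with a 'No' and an empty set of daily records is kept as a non-reactor. A child with a 'Yes' and no known grade is not kept as a reactor.

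At stake is the solicited reaction rate by group. It is part of the safety profile that, according to SAP Section 1, may support the planned Phase III study. With about 50 children per group, a single child can decide whether an uncommon reaction appears in the table at all.

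**Working it through.** The plan states no figure to reproduce: the sample size rests on feasibility and no hypothesis is tested (SAP 3.1 and 3.2). The check is therefore a trace of the rules followed by an illustration.

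**Step 1. Trace of the rules for one non-measurable reaction over the solicited period (D01 to D22 after dose 1).**

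| CRF presence and daily records | Maximum (4.2.4.1.2) | Presence (4.2.4.1.3) | Effect |
|---|---|---|---|
| 'No', all days missing | None, by the stated rule | No presence | kept in denominator |
| 'Yes', all days unknown or missing | Missing | Missing | leaves numerator and denominator |
| 'Yes', one day unknown, other days None | not defined; None if missing values are ignored | not defined; No presence if missing values are ignored | depends on programming |
| 'Yes', one day unknown, another day Grade 1 or higher | Grade 1 or higher | Presence | counted correctly |

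Rows 1 and 2 follow from the text. Row 3 is a gap in the text. Section 4.2.4.3 has the same gap for the after-any-vaccination tables, when one dose gives Missing and the other None.

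**Step 2. Direction.** Let N children include x with the reaction, of whom k have no known grade on any day (k at least 1, k below N).

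- Counting them as present: x/N.
- Dropping them (row 2): (x − k)/(N − k). This is below x/N when N(x − k) < x(N − k), which reduces to x < N. The rate therefore falls unless every child reacted, and it never rises.
- If missing values are ignored (row 3): (x − k)/N, which is always below x/N.

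**Step 3. Illustration.** N = 50 per group is the planned size (SAP 3.2). The values of x and k are assumptions, since the documents give neither. Intervals are two-sided 95% Clopper-Pearson, the SAP's method (3.4.1): lower limit is the 0.025 quantile of Beta(x, n − x + 1), upper limit the 0.975 quantile of Beta(x + 1, n − x). With no events the lower limit is 0 and the upper is 1 − 0.025^(1/n).

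| Assumed x, k | Counted as present | Dropped (row 2) | Counted as none (row 3, if missing ignored) |
|---|---|---|---|
| 1, 1 | 1/50 = 2.0% (0.05 to 10.65) | 0/49 = 0% (0 to 7.25) | 0/50 = 0% (0 to 7.11) |
| 5, 2 | 5/50 = 10.0% (3.33 to 21.81) | 3/48 = 6.25% (1.31 to 17.20) | 3/50 = 6.0% (1.25 to 16.55) |
| 20, 3 | 20/50 = 40.0% (26.41 to 54.82) | 17/47 = 36.2% (22.67 to 51.48) | 17/50 = 34.0% (21.21 to 48.77) |

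In the last two rows the altered rate stays well inside the interval around the full count. In the first row the only observed case disappears.

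**The case against.** The best defence is that grade-based presence is a reasonable convention for pre-listed terms. Lost appetite, for example, is defined in Protocol Table 10.2 by its intensity scale. Data collection also limits the loss: the diary card is reviewed at V02 to V08 after dose 1 and at V09 to V11 after dose 2, with an instruction to resolve incomplete entries, and listings must show missing data as missing (SAP 3.4.6.1). All of this stands and makes the case less frequent. It does not explain why the CRF answer is trusted when it is 'No' and ignored when it is 'Yes'.

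A reader might infer more than the documents support:

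- *Every unknown grade lowers the rate.* It does not. One day at Grade 1 or higher restores presence, and in a summary of any solicited reaction another graded reaction would presumably still count the child.
- *An ungraded reactor is counted as having no reaction.* That depends on the ranking of Missing against None, which the SAP leaves open.
- *Any daily 'unknown' is a reaction.* The CRF is not in the documents. Since grades are transcribed from the diary card, 'unknown' may only mean that the day was not filled in.
- *A withdrawal for an ungraded solicited reaction goes uncounted.* Under SAP 4.2.5.6 the disposition and safety overview tables can both count the child through the End of Study form. Mainly the SOC/PT table depends on the grade.
- *The vaccine-placebo difference is narrowed.* That needs an assumption about the share of ungraded reactors in each arm, on which the documents are silent.

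The contrast with unsolicited AEs is not fully like for like, because those exist through a verbatim term. It still shows that the SAP accepts an event without a grade elsewhere.

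**Conclusion.** The point holds in a limited form. For non-measurable solicited reactions, the SAP's stated rules remove a child whose CRF presence is 'Yes' and whose daily grades are all unknown or missing, while keeping a child with 'No' and missing records. For such cases the reported rate can only go down. Where the unknown day sits among days graded None, the outcome is undefined rather than wrong.

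The size cannot be estimated from the documents and may be small. The illustration rests on assumed counts of reactors and ungraded reactors; only the 50 per group and the interval method come from the SAP. The consequence is clearest for rare reactions, where one ungraded case turns 1/50 into 0/49. Fever is outside the point, because it is graded from the recorded temperature.

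**What to change.** 1. **SAP 4.2.4.1.1 and 4.2.4.1.3.** For non-measurable solicited reactions, if the CRF presence answer is 'Yes' and no daily grade is 1 or higher, set presence to Presence and maximum intensity to Missing, and keep the child in numerator and denominator. Do not treat a daily 'unknown' without a CRF 'Yes' as a reaction.
2. **SAP 4.2.4.1.2 and 4.2.4.3.** State how Missing ranks against None, both across days and across doses.
3. **Displays.** Add a Missing category to maximum intensity, time of onset (4.2.4.1.4) and number of days (4.2.4.1.5). The last two are defined by Grade 1 or higher and would otherwise have no value for these children.
4. **SAP 4.2.5.6.** Count a solicited AE that caused study termination when its grade is at least 1 or missing, as for unsolicited AEs. This mainly changes the SOC/PT table.
5. **Fever.** Leave it based on the measured temperature.

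The cost is a few sentences in the SAP, a few extra table categories and slightly higher stated reaction rates. On the SAP's own description the CRF presence answer is already recorded, so no new data collection and no change to clinical procedures is needed.

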#### 4.2.4.1.4 Time of Onset

Time of onset is derived from the daily intensities computed as described in [Section 4.2.4.1.1](#). It corresponds to the first day with intensity of Grade  $\geq 1$ .

Note: If a reaction is not continuous (i.e., reaction occurs over two separate periods of time intervened by at least one daily intensity Missing or None) then the time of onset is the first day of the first occurrence.

Time of onset period is displayed as D01-D04, D05-D08, D09-D15, D16-D22

#### 4.2.4.1.5 Number of Days of Occurrence During the Solicited Period

Number of days of presence over the period considered is derived from the daily intensities computed as described in [Section 4.2.4.1.1](#). It corresponds to the number of days with daily intensities of Grade  $\geq 1$ . Number of days of presence on the solicited period with a specified intensity may also be derived.

Number of days of presence during the solicited period is displayed as 1-3 days, 4-7 days, 8-14 days, 15-21 days, 22 days.

#### 4.2.4.1.6 Overall Number of Days of Occurrence/ Presence

If a reaction is ongoing at the end of the solicited period, then the overall number of days of presence is derived from the daily intensities and the end date of the reaction after the end of the solicited period. The overall number of days of presence is:

- $(\text{end date} - \text{last vaccination date}) + (\text{number of days of presence within the solicited period}) - \text{length of the solicited period} + 1$

If the end date is missing or incomplete (contains missing data [MD]), the overall number of days of presence will be considered as Missing.

Overall number of days of presence is displayed as 2-3 days, 4-7 days, 8-14 days, 15-21 days, 22 days or more, and Missing end date.

#### 4.2.4.1.7 Ongoing

Ongoing is derived from the last daily intensity of the solicited period computed as described in [Section 4.2.4.1.1](#) and the maximum intensity on the ongoing period. The investigator's ongoing flag is not used because the measurement would determine the ongoing status of the reaction. Note the intensity could be considered None (not a reaction) in the analysis despite being considered a reaction by the investigator.

- Ongoing: if the last daily intensity of the solicited period is at least Grade 1 and the maximum intensity on the ongoing period is at least Grade 1
- Not ongoing: if the last daily intensity of the solicited period is None or the maximum intensity on the ongoing period is None.
- Missing: all other conditions (in this case, it is not included in the denominator of the ongoing analysis in the safety tables).

#### 4.2.4.2 Unsolicited AEs

##### 4.2.4.2.1 Presence

An observation will be considered an event if it has at least a verbatim term and is not a Grade 0 intensity event.

Grade 0 events are not included in safety analysis but are included in separate listings.

##### 4.2.4.2.2 Intensity

Intensity will be derived according to the following classification: None, Grade 1, Grade 2, Grade 3, or Missing.

If the unsolicited AE is measurable and its preferred term is part of the list of solicited reactions, then the measurement is derived based upon and following the same rule than the intensity scales defined in Table 10.1 and 10.2 of the protocol for that measurable solicited reaction. Note the intensity could be considered “None” (not a reaction) in the analysis despite being considered a reaction by the investigator.

Intensity for the other unsolicited AEs will correspond to the value reported in the eCRF.

The maximum intensity corresponds to the highest intensity for a unique term.

##### 4.2.4.2.3 Last Vaccination

Last vaccination before an unsolicited AE is derived from the start date of the unsolicited AE provided in the eCRF and is calculated as follows:

- If an unsolicited AE has a complete start date and different to any of the vaccination dates, the start date is used to determine the last vaccination before the unsolicited AE

If the start date is missing or partially missing, or equal to any vaccination date, then the visit number in the “Appeared after Visit” or similar field, is used to determine the last vaccination before the unsolicited AE

##### 4.2.4.2.4 Time of Onset

Time of onset is derived from the start date of the unsolicited AE and the date of last vaccination as described in [Section 4.2.4.2.3](#):

- start date of the unsolicited AE – date of last vaccination before the unsolicited AE

The time of onset is considered as missing only if one or both dates are missing or partially missing.

The unsolicited AEs will be analyzed “within 28 days” after each vaccination (i.e. acute phase), which corresponds to AEs with a time of onset between D01 and D29 days. An AE with missing time of onset will be considered to have occurred just after the last vaccination (computed according to the [Section 4.2.4.2.3](#)), so will be included in these tables.

Time of onset period is displayed as D01-D04, D05-D08, D09-D15, D16 or later, and Missing.

Note: Unsolicited AE that occurred before vaccination (negative time of onset) or with a time of onset higher than defined above will not be included in analysis but will be listed separately

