Control method	Placebo-controlled
Study population	
• Pediatric participants: Healthy infants / toddlers 6 to < 24 months of age in close contact with other infants / toddlers 6 to < 24 months of age who participate in the study• Ad-hoc close contact participants: ad-hoc close contact children and adults who experience acute respiratory illness (ARI) in the 28 days following the administration of the study intervention to the close contact pediatric participant
Countries	United States and Puerto Rico
Level and method of blinding	Observer-blind: 
• Blinding for vaccine group assignment: participants, parents or legally acceptable representative (LAR), outcome assessors, investigators, laboratory personnel, Sponsor study staff• No blinding for study staff who prepare and administer the study interventions
Study intervention assignment method	Pediatric participants will be screened for eligibility criteria at the time of inclusion and randomized to receive either RSVt vaccine or placebo in a 1:1 ratio

Brief Summary:

The primary purpose of the VAD00014 study is to assess the shedding, transmission, and genetic stability of the live-attenuated RSVt vaccine after each intranasal vaccination (56 days apart) in infants and toddlers 6 to < 24 months of age. Study details include:

The study duration will be:

- up to 8 months, including the 6 months safety follow-up phone call after the second study intervention administration for the pediatric participants

The treatment administration for the pediatric participants will be on D01 and D57 (1 intranasal administration each).

The visit frequency will be twice a week after D01 (ie, first administration of study intervention) up to D22 for a total of 7 visits (D01, D04, D08, D11, D15, D18, and D22), and 7, 14, and 28 days after D57 (second administration) at D64, D71, and D85. Some of these visits may be managed as home visits or daycare center visits.

Additional illness visits may occur during the study intervention phase (D01-D85) in case of acute respiratory symptoms.

Number of Participants:

A total of 100 pediatric participants are expected to be randomized (50 participants in each study intervention group).

Intervention Groups and Duration:

Eligible pediatric participants will be randomized in a 1:1 ratio to receive 2 intranasal administrations (56 days apart) of either the RSVt vaccine or placebo at D01 and D57.

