8.3.1 Time Period and Frequency for Collecting AE and SAE Information

Immediate Post-vaccination Observation Period

Participants will be kept under observation for 30 minutes after each vaccination to ensure their safety. The post-vaccination observation should be documented in the source document.

Reactogenicity

Solicited administration site reactions will be collected from the day of vaccination until 21 days after each vaccination (D01 to D22 and D57 to D78).

Solicited systemic reactions will be collected from the day of vaccination until 21 days after each vaccination (D01 to D22 and D57 to D78).

The solicited administration site reactions and systemic reactions that are pre-listed in the diary cards and CRF, together with the intensity scales, are presented in [Appendix 10.2.5.1.1](#).

Reactogenicity is to be reported only for IMPs. Refer to [Table 6.1](#) to know which study interventions are considered as IMPs.

Unsolicited Non-serious Adverse Events

Unsolicited non-serious adverse events will be collected from the day of vaccination until 28 days after each vaccination (D01 to D29 and D57 to D85).

The intensity grading scale for unsolicited non-serious adverse events is presented in [Appendix 10.2.5.1.2](#).

Medically Attended Adverse Events (MAAEs)

MAAEs will be collected from the day of vaccination until 28 days after each vaccination (D01 to D29 and D57 to D85).

Adverse Events of Special Interest (AESIs)

AESIs will be collected from the day of vaccination until 28 days after each vaccination (D01 to D29 and D57 to D85).

See [Section 8.3.6](#) for the list of AESIs.

SAEs

Information on SAEs will be collected and assessed throughout the study, from D01 until 180 days after the last vaccination. However, before the first study intervention administration, only SAEs related to study procedures are to be collected in the CRF.

All SAEs will be recorded and reported to the Sponsor or designee immediately and under no circumstance should this exceed 24 hours, as indicated in [Appendix 10.2](#). The investigator will submit any updated SAE data to the Sponsor within 24 hours of it being available.

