#### **4.2.4.2.5 Duration**

Duration is derived from the start and end dates of the unsolicited AE:

- end date of unsolicited AE – start date of unsolicited AE + 1.

The duration is considered as missing only if one or both of the start and end dates of the unsolicited AE is missing or partially missing.

Duration period is displayed as 1-3 days, 4-7 days, 8-14 days, 15 or more, and Missing

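### SAP 4.2.4.2.4 computes onset of unsolicited AEs on a scale where the vaccination day is 0, but sets the 28-day window and display bins on a scale where it is D01

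*SAP*

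**What the plan says.** SAP 4.2.4.2.4 (Time of Onset, unsolicited AEs) gives four rules.

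- Formula: "start date of the unsolicited AE – date of last vaccination before the unsolicited AE".
- Exclusions: the section's Note says which events leave the analysis and are only listed. It reads: "Unsolicited AE that occurred before vaccination (negative time of onset) or with a time of onset higher than defined above will not be included in".
- Window: the 28-day analysis is the one "which corresponds to AEs with a time of onset between D01 and D29 days".
- Display: the onset bins are D01-D04, then D05-D08, then D09-D15, then everything from D16 on, with a further category for missing onset. There is no bin for 0.

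The protocol fixes the day scale. In the Synopsis, D01 is the day of the first dose: "The visit frequency will be twice a week after D01 (ie, first administration of study intervention) up to D22". In section 8.3.1, "Unsolicited non-serious adverse events will be collected from the day of vaccination until 28 days after each vaccination (D01 to D29 and D57 to D85"); AESIs and MAAEs have the same period. SAEs are collected until 180 days after the last vaccination.

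SAP 3.4.3.2 and 4.2.4.2.7 tabulate SAEs within 28 days of any vaccination as well as over the whole study. Immediate events have a separate 30-minute summary (SAP 3.4.3.2), identified by a CRF field for immediate events (SAP 3.4.6.1.1).

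**The concern.** The window D01-D29 is right on the protocol's scale, where the vaccination day is day 1. The formula is on a different scale, where the vaccination day is 0. The SAP does not say how one converts to the other.

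A programmer who applies the text as numbers would find that an event starting on the vaccination day (onset 0) is below the window and has no display bin, while an event 29 days after dosing (onset 29) is inside. Unsolicited AEs, AESIs and MAAEs within 28 days are secondary safety endpoints, and vaccination-day events are those closest in time to dosing. Two competent programmers could produce different safety tables from the same section.

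**Working it through.** **Inputs.** Formula, window, bins and Note: SAP 4.2.4.2.4. Day labels: D01 is dose 1 and D57 is dose 2 (Protocol Synopsis). Protocol window: vaccination day to 28 days after (Protocol 8.3.1).

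**Step 1: the two scales.** Let k be the number of calendar days from the last dose to the start of the event.

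- Protocol day = 1 + k after dose 1, and 57 + k after dose 2.
- SAP time of onset = k.

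The protocol window is k = 0 to 28, which is D01-D29 (29 − 1 + 1 = 29 days) and D57-D85 (85 − 57 + 1 = 29 days).

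**Step 2: try to reproduce the window from the SAP text.**

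| Reading | k kept | Dose 1 | Dose 2 | Days | Against the protocol |
|---|---|---|---|---|---|
| Protocol 8.3.1 | 0-28 | D01-D29 | D57-D85 | 29 | reference |
| SAP window as numbers 1 to 29 | 1-29 | D02-D30 | D58-D86 | 29 | loses D01 and D57, gains D30 and D86 |
| SAP Note alone (drop below 0 or above 29) | 0-29 | D01-D30 | D57-D86 | 30 | gains D30 and D86; onset 0 has no bin |
| Formula + 1, window 1 to 29 | 0-28 | D01-D29 | D57-D85 | 29 | matches |
| Formula unchanged, window 0 to 28 | 0-28 | D01-D29 | D57-D85 | 29 | matches, but bins must also start at 0 |

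Neither numeric reading of the present text returns the stated window.

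**Step 3: the bins.** Computed onset is study day minus 1 (counting the vaccination day as study day 1).

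- Study day 1: 0, no bin.
- Study day 5: 4, shown in D01-D04 instead of D05-D08.
- Study day 9: 8, shown in D05-D08 instead of D09-D15.
- Study day 16: 15, shown in D09-D15 instead of D16 or later.

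Every onset is one day early, but only events on the first day of a bin change category. For tables over any vaccination, SAP 4.2.4.3 takes the smallest onset across doses, so a 0 would be selected and then have nowhere to go.

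**Step 4: practice elsewhere in the SAP.** Unsolicited AE duration is "end date of unsolicited AE – start date of unsolicited AE + 1". SAP 4.2.4.1.6, for solicited reactions, counts from the vaccination date and also adds 1. For a reaction present D01-D22 and ending on D25, with a 22-day solicited period, it gives (25 − 1) + 22 − 22 + 1 = 25 days, which is correct with the vaccination day as day 1.

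**Step 5: size.** Per dose, one of 29 eligible days is lost under the numeric window, and one ineligible day is gained under either reading. With 50 participants planned per group, one participant moved in or out of a table changes a percentage by 1/50 = 2 points.

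**The case against.** The strongest reply is that D01 and D29 are the protocol's day labels, not the integers 1 and 29. A difference of 0 is then D01, a difference of 28 is D29, and nothing is lost, gained or shifted. Other text points to the same intent. The Note excludes only negative and too-high onsets, and 0 is neither. Events with a missing onset are treated as starting just after vaccination and are kept in the tables. SAP 4.2.4.2.3 has a rule for assigning events that start on a vaccination date to a dose. A plain difference is also a normal way to express elapsed time, so the missing 1 is not an error by itself.

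Much of this stands as evidence of intent. A reader might infer that vaccination-day events, and with them every immediate AE, are definitely excluded. The documents do not support that: the section contradicts itself about onset 0, and immediate AEs have a summary that does not use onset in days. They are at risk only in the 28-day and onset tables. A reader might also infer that D29 events enter wrongly. They do not: D29 is 28 days after dosing and belongs in the window. The day wrongly admitted is D30 or D86. Because planned collection of unsolicited non-serious AEs, AESIs and MAAEs ends at D29 and D85, mainly SAEs could enter that way. SAEs also stay in the whole-study table, and excluded events are listed.

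The reply does not remove the problem. The SAP never states the label mapping. Its Note treats onset as a number that can be negative, and section 4.2.4.1.6 adds 1 when counting from the same date. If the Note is followed instead of the numeric window, 30 days are still admitted and onset 0 still has no bin.

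**Conclusion.** The onset formula and the window are on different day scales, and neither numeric reading of the section gives the protocol's D01-D29 and D57-D85. With the window taken as numbers, the 28-day tables lose vaccination-day unsolicited AEs, AESIs, MAAEs and SAEs. With the Note taken alone, those events stay but cannot be displayed by onset. Under both, an event 29 days after dosing qualifies and events on study days 5, 9 and 16 are shown one bin early.

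The size depends on how many events start on those particular days, which the documents do not give. Loss of vaccination-day events is a possible result of a contradictory rule, not a certain one. The conclusion assumes that the section's onset definition governs AESIs, MAAEs and the 28-day SAE table, since the SAP places all three under unsolicited AEs and gives no other definition. The derivation should be corrected; the design is not affected.

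**What to change.** In SAP 4.2.4.2.4:

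- Define time of onset as AE start date minus date of last vaccination, plus 1. Keep the D01-D29 window and the bins unchanged.
- Reword the Note. After the change, the day before vaccination computes to −1 + 1 = 0, which is no longer negative. Pre-vaccination should mean an onset below D01, or a start on the vaccination date but before dosing as decided by the existing Appeared after Visit rule in SAP 4.2.4.2.3.
- State that post-dose events on the vaccination day are included and count as D01.

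Keeping the plain difference and writing the window as 0 to 28 selects the same days, but then the bins must be rewritten to start at 0, so adding 1 is the smaller edit.

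The cost is one term in a formula, one reworded Note and one added sentence, with no change to the protocol or data collection. Interim safety tables that use this derivation should be checked against the corrected rule.
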